10. OTHER ANALYSIS

- 11.1 Blinding assessment

An additional assessment using the Bang Blinding Index will be performed to determine whether the study blinding has been maintained. The Bang Blinding index is on a scale of 0 to 1 where 0 indicates complete lack of blinding and 1 indicates perfect blind. 95% confidence intervals will also be presented.

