## 2. Protocol Synopsis

Title	A prospective, double-blind, sham-controlled, randomized clinical trial to assess the safety and efficacy of the Mi-Helper Device for acute treatment of migraine in an at home setting.
Short Title	Cooling to Alleviate Migraine #3 (CALM-3)
Clinical Study Type	Non-Significant Risk (NSR) Device Study
Product Name	Mi-Helper Device
Study Duration	~7 months
Country of Implementation	USA
Description of Sites	One decentralized site
Study Objectives	
Primary Objectives:
 
 
To determine the safety and efficacy of one dose of Mi-Helper therapy compared to sham for the acute treatment of a single migraine attack.
 
 
Secondary Objectives:
 
 
To assess the tolerability of the Mi-Helper device, based on the percentage of participants who fail to complete the full treatment session.
 
To assess sustained pain freedom between 2 and 24 hours post treatment completion without the use of rescue medication.
 

	
 
• To determine the proportion of participants reporting pain relief after Mi-Helper therapy without the use of rescue medication.
 
• To determine the effect of Mi-Helper therapy on the most bothersome symptom (MBS) other than headache post treatment completion.
 
 
Exploratory Objectives:
 
 
• To explore the use of rescue medication following a single therapeutic treatment.
 
• To assess whether blinding was maintained from a participant's perspective.
 
• To assess sustained pain freedom and sustained pain relief from 2 to 48 hours post treatment completion without the use of rescue medication.
 

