### 11.9 Blinding Assessment

An additional assessment using the Blinding Index will be performed to determine whether the study blinding has been maintained. The Blinding index is on a scale of 0 to 1 where 0 indicates complete lack of blinding and 1 indicates perfect blind. 95% confidence intervals will also be presented.

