3.1.3. Exploratory Objectives

- To explore the use of rescue medication following a single therapeutic treatment
- To assess whether blinding was maintained from a participant's perspective
- To assess sustained pain freedom from 2 to 48 hours post treatment completion without the use of rescue medication
- To assess effect of Mi-Helper therapy on migraine associated symptoms (nausea, photophobia, and phonophobia).

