5. SAMPLE SIZE CALCULATION

The sample size for this study was calculated to test the null hypothesis with a two-tailed Fisher's exact test.

The sample size is calculated to test the null hypothesis with 80% power at a 5% level of significance using PASS 2024 software, version 24.0.2.

If we assume that 41% of the participants in the active treatment arm will have pain freedom at 2 hours post treatment versus 16% in the sham arm, then 116 evaluable participants are required (58 per group). Allowing for a 25% dropout rate, a total of 156 (78 active versus 78 sham) participants should be enrolled in the study.

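### SAP 10 names the Bang blinding index but gives it a 0 to 1 scale that is not Bang's, so either the name or the scale is wrong

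*SAP*

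**What the plan says.** SAP 10 commits to a named method: "An additional assessment using the Bang Blinding Index will be performed to determine whether the study blinding has been maintained". It then gives the scale: "The Bang Blinding index is on a scale of 0 to 1 where 0 indicates complete lack of blinding and 1 indicates perfect blind". It adds: "95% confidence intervals will also be presented".

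Protocol 11.9 plans the same assessment without naming an index: "An additional assessment using the Blinding Index will be performed to determine whether the study blinding has been maintained". Its scale is identical: "The Blinding index is on a scale of 0 to 1 where 0 indicates complete lack of blinding and 1 indicates perfect blind".

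Neither document gives a formula, says whether the index is per arm or for the whole trial, or sets a threshold for reading it. The purpose is listed among the exploratory objectives in SAP 3.1.3, "To assess whether blinding was maintained from a participant's perspective", and in the protocol synopsis.

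**The concern.** The Bang index is positive when participants guess their own arm correctly more often than not. Zero is what a working blind produces, and +1 is total unblinding. The SAP attaches the opposite meanings to 0 and 1 and leaves out the negative half of the range. If an analyst computes Bang and reads it with the SAP's key, complete unblinding is reported as an ideal blind and chance guessing as no blinding. Between those two anchors the values run in the wrong direction.

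This matters because the outcomes are self-reported in the app, and the arms differ in ways a participant might feel: 10 LPM continuous flow against 2 LPM or less with the blower cycling on and off (Protocol 5 and 7.1.1). Protocol 3.2 already cites a blinding index from the earlier dosing study as evidence that blinding succeeded, so this result is likely to be cited too.

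**Working it through.** **Inputs.** The index name is from SAP 10. The scale is from SAP 10 and Protocol 11.9. The arm size of 58 is the evaluable number per group in SAP 5, used here as an assumed number of answers. All guess counts are assumptions, since the documents give none.

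**Formulas.** Let c, w and d be the correct, wrong and 'don't know' answers in an arm, with n = c + w + d, p1 = c/n and p2 = w/n.

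- Bang, one value per arm: B = (c - w)/n, with variance [p1(1 - p1) + p2(1 - p2) + 2·p1·p2]/n and 95% CI B ± 1.96 SE.
- James, one value for the trial: J = [1 + P_DK + (1 - P_DK)·K]/2. P_DK is the 'don't know' proportion. K = (observed - expected)/expected disagreement among those who guess, with weight 0 for a correct and 0.5 for a wrong guess.

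**Step 1: can the stated scale be reproduced?** With the same pattern in both arms, n = 58:

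| Pattern | Bang | James |
|---|---|---|
| all correct | 58/58 = +1 | 0 |
| half correct, half wrong | 0/58 = 0 | 0.5 |
| all 'don't know' | 0/58 = 0 | 1 |
| all wrong | -58/58 = -1 | 1 |

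The SAP's key (0 = no blinding, 1 = ideal blind, nothing below 0) does not come out of Bang. It does fit James.

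**Step 2: intermediate patterns.** One case in full, 46 correct and 12 wrong in each arm:

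- Bang: (46 - 12)/58 = 0.586. With p1 = 0.793 and p2 = 0.207, the variance is (0.164 + 0.164 + 0.328)/58 = 0.0113, so SE = 0.106 and the CI is 0.378 to 0.795.
- James: observed disagreement 0.5 × 0.207 = 0.103; expected 0.5 × 0.5 = 0.25; K = (0.103 - 0.25)/0.25 = -0.586; J = (1 - 0.586)/2 = 0.207.

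| Correct/wrong/'don't know' per arm | Bang (95% CI) | James |
|---|---|---|
| 46/12/0 | 0.586 (0.378 to 0.795) | 0.207 |
| 35/23/0 | 0.207 (-0.045 to 0.459) | 0.397 |
| 29/29/0 | 0.000 (-0.257 to 0.257) | 0.500 |
| 37/9/12 | 0.483 (0.290 to 0.675) | 0.362 |
| 23/23/12 | 0.000 (-0.229 to 0.229) | 0.603 |
| active 46/12/0, sham 12/46/0 (most guess active in both arms) | +0.586 and -0.586 (-0.795 to -0.378) | 0.500 |

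In the last row the whole sham interval lies off the stated scale. Whenever Bang is 0 and anyone has guessed, its interval extends below 0. Not every pattern flips about the midpoint: with 37/9/12 both indices lie below 0.5.

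**Step 3: how often would Bang fall off the scale?** Suppose blinding is ideal and each of 58 guesses is 50:50.

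- One arm: P(B < 0) = P(Bin(58, 0.5) ≤ 28) = 0.448.
- At least one of two arms: 1 - (1 - 0.448)² = 0.695. With 46 guessers per arm it is 0.688, and with 78 it is 0.703.

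If instead everyone guesses active with probability 0.6, the sham value is negative with probability P(Bin(58, 0.4) ≤ 28) = 0.921 (0.953 with 78 per arm).

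**The case against.** The strongest reply concerns weight, since nothing in either document rescues the sentence. Blinding is not in the endpoint lists (Protocol 4, SAP 3.2.4). The Amendment 2 log records removal of a blinding objective and endpoint, so the objective lines that remain may be carry-over text. A competent analyst would probably notice: a negative value on a scale that starts at 0 exposes the error at once. If James was intended, only one word is wrong. The worked figures show how the two indices behave and do not predict this trial's result.

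Most of that stands, and it limits the importance of the point without removing it. The analysis is still planned in Protocol 11.9 and SAP 10. An analyst who notices must depart from either the name or the scale, and should not make that choice after seeing the guesses.

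Two further remarks also stand. The documents do not show the treatment-guess question, its response options or its timing. It may sit in the user experience questionnaire, whose content is not given, so it cannot be called missing. The two indices do treat 'don't know' answers differently, so the choice depends on those options. And a protocol edit is not free (Protocol 12.2 and 13.2).

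**Conclusion.** The SAP sentence is wrong as written, because the scale and both anchor meanings contradict the definition of the index it names. The documents do not settle whether the name or the scale is the mistake. The reversal is exact only at 0 and 1; between them the direction is wrong, and negative values have no meaning on the stated scale. With about 46 to 78 guessers per arm and ideal blinding, a negative Bang value in at least one arm has probability of about 0.69 to 0.70. That rests on 50:50 guessing, independence between arms and assumed response numbers.

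The consequence could be a misreported or uninterpretable blinding result. The significance level, sample size, and efficacy and safety tests are untouched. It should be corrected, but it is a modest point.

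**What to change.** Before unblinding, settle on one index and give it its own scale. There are two options.

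- **Keep Bang.** Report it per arm with its 95% CI on -1 to +1 (0 = chance guessing, +1 = all correct, -1 = all opposite). The scale in Protocol 11.9 must then change as well.
- **Name James and keep 0 to 1.** State that chance guessing with no 'don't know' answers gives 0.5, not 1. The scale in Protocol 11.9 is then compatible; naming James there as well would align the two documents.

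State the guess question's response options at the same time, since both indices need them.

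The trade-off is that Bang shows when both arms mostly guess active, while James returns a single 0.50 for that pattern and hides it. The cost is one sentence in the SAP and one in the protocol, with no change to any efficacy or safety test. A protocol edit has to follow the amendment route in Protocol 12.2, and Protocol 13.2 asks active participants to re-sign consent after an amendment. Under the James option the essential correction can be made in the SAP alone.

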11. REPORTING

11.1. Statistical Analysis Output

A Statistical Analysis Outputs will be developed and provided by SPRIM PRO. The report will include all required results in tables, listings, and figures agreed upon in the TLF Shells document. The Statistical Analysis Outputs will be output as either one file compiling all tables, listings, and figures, or a zip folder that houses the output items in separate files.

11.2. Clinical Study Report

A Clinical Study Report will be developed and provided by SPRIM PRO blinded statisticians after database lock, delivery of the statistical analysis, and the TLF deliverable is approved by the client. The report will address study background, methodology, and all required results including tables, listings, and figures agreed upon in the SAP.

